## 2. INTRODUCTION AND STUDY OVERVIEW

The purpose of this statistical analysis plan (SAP) is to describe the planned analyses of data from GBT440-007 Part D.

Where applicable, the statistical analysis methods presented in this document will supersede the statistical analysis methods described in the study protocol.

### Study Overview:

GBT440-007 is a multicenter, open-label study to evaluate the safety, pharmacokinetics (PK) and efficacy of voxelotor in pediatric subjects with Sickle Cell Disease (SCD).

This study consists of 4 parts, Part A, Part B, Part C, and Part D. The planned analyses of data from Part D are described in this SAP.

Part D assesses the safety, tolerability, and PK, as well as the hematological effects of voxelotor in pediatric subjects with SCD who are 6 months to < 4 years of age. Approximately 30 pediatric subjects will be enrolled into Part D.

## 3. STUDY OBJECTIVES FOR PART D

### 3.1. Primary

- To evaluate the safety and tolerability of voxelotor in pediatric subjects with SCD aged 6 months to < 4 years

### 3.2. Secondary

- To characterize the PK of voxelotor in plasma, whole blood, and red blood cells (RBCs) in pediatric subjects with SCD aged 6 months to < 4 years
- To evaluate the effect of voxelotor on clinical measures of anemia and hemolysis in pediatric subjects with SCD aged 6 months to < 4 years
- To evaluate the effect of voxelotor on the incidence of stroke and vaso-occlusive crisis (VOC) in pediatric subjects with SCD aged 6 months to < 4 years

### 3.3. Exploratory

- To evaluate the effect of voxelotor on growth and development pediatric subjects with SCD aged 6 months to < 4 years

## 4. ENDPOINTS FOR PART D

### 4.1. Primary

- Treatment-emergent adverse events (TEAEs) and serious adverse events (SAEs)

### 4.2. Secondary

- Whole blood and plasma voxelotor PK (maximum blood concentration [ $C_{max}$ ], area under the concentration-time curve [AUC], terminal elimination half-life [ $t_{1/2}$ ], if appropriate) and percent hemoglobin (Hb) occupancy
- Change from baseline to Week 24 and Week 48 in Hb, lactate dehydrogenase (LDH), indirect bilirubin, and reticulocyte count
- Time to initial Hb response, with Hb response defined as change from baseline in Hb  $> 1\text{g/dL}$ 
  - Time to initial Hb response is defined as time from first dose of study treatment to first occurrence of change from baseline in Hb  $> 1\text{g/dL}$
- Incidence of stroke and VOC during the study
- In addition to the protocol-specified secondary endpoints, Hb response (defined as a change from baseline in Hb  $> 1\text{g/dL}$ ) will be assessed at both Week 24 and Week 48.

### 4.3. Exploratory

- Growth and development as assessed by change from baseline to Weeks 24 and 48 in height, weight, and head circumference

### 4.4. Safety

- Clinical laboratory tests and vital signs

## 5. DEFINITIONS AND TERMINOLOGY

### Study Day

Study Day is defined relative to initiation of treatment, i.e., Day 1. Thus, the study day of an event is calculated as:

$$\text{Study Day} = \text{event date} - \text{Day 1 date} + 1.$$

### Study Visit

Study Visit is the nominal visit as recorded on the Case Report Form (CRF).

## Baseline

For all endpoints where both Screening and Day 1 pre-dose assessments are collected, baseline is defined as average of all assessments prior to the first dose. If there is an unscheduled visit prior to first dose, this unscheduled assessment will also be included in the baseline calculation.

## Change from Baseline

Change from baseline to follow-up visit will be calculated as the baseline measurement subtracted from the follow-up measurement for all assessments. Percent change from baseline values to post-baseline values will be calculated using the following formula where applicable:

$$([post\text{-}baseline\ value - baseline\ value] / baseline\ value) \times 100\%$$

## Exposure to Study Drug

Duration of exposure to study drug is defined as the number of weeks from Day 1 to the last date of dosing of study drug. The derivation is as follows:

$$(\text{Last dose date} - \text{First dose date} + 1)/7$$

Actual exposure to study drug is defined as the number of weeks from Day 1 to the last date of dosing of study drug which excludes days where treatment was entirely missed or intermittently stopped as recorded in the CRF. The derivation is as follows:

$$(\text{Last dose date} - \text{First dose date} - \text{Number of days study drug was not taken} + 1)/7$$

## Prior Medications

Prior medications are those medications taken prior to the initiation of study drug.

## Concomitant Medications

Concomitant medications are those medications taken on or after the initiation of study drug. This definition includes medications started prior to the initiation of study drug, but continuing concurrently with study drug.

RBC transfusions are collected as concomitant medications.

## Hemoglobin Response

Hb response is defined as an increase in Hb > 1 g/dL from Baseline and will be assessed at both Week 24 and Week 48.

## Treatment-Emergent Adverse Event

A treatment-emergent adverse event (TEAE) is defined as an adverse event (AE) that emerges on or after initiation of study drug (having been absent pre-treatment), or an AE that existed pre-treatment and worsened on treatment (relative to the pre-treatment state) through 28 days after study drug discontinuation.

## 6. GENERAL STATISTICAL CONSIDERATIONS

### 6.1. Sample Size Considerations

Approximately 30 pediatric subjects with SCD who are 6 months to < 4 years of age will be enrolled in GBT440-007 Part D. The sample size was selected to provide descriptive assessment of safety, tolerability, and PK effects of voxelotol in this younger age group with no formal statistical assumptions.

### 6.2. Handling of Missing or Partial Dates

#### 6.2.1. Missing Start Dates for Prior and Concomitant Medication

For missing start day only: day will be imputed as the first day of the month (i.e., 1) with the following exception: If the partial date falls in the same month and year as the treatment start date then the concomitant medication start date will be imputed as the treatment start date.

For missing start day and month: day and month will be imputed as the first day of the year (i.e., 1 January) with the following exception: If the partial date falls in the same year as the treatment start date then the concomitant medication start date will be imputed as the treatment start date.

#### 6.2.2. Missing Start Dates for Adverse Events

For missing start day only: day will be imputed as the first day of the month (i.e., 1) with the following exception: If the partial date falls in the same month and year as the treatment start date then the adverse event start date will be imputed as the day prior to the treatment start date.

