3.9.4. Endpoints for Part D

3.9.4.1. Primary Endpoints

- TEAEs and SAEs

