### **6.2.3. Missing Start and Stop Dates for Adverse Events**

For missing start day only: Day will be imputed as the first day of the month (i.e., 1) with the following exception: If the partial date falls in the same month and year as the treatment start date then the adverse event start date will be imputed as the day prior to the treatment start date.

For missing stop day only – Day only will be imputed as the last day of the month (i.e., 28, 29, 30, or 31).

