### **8.3.2. Adverse Events**

Adverse events reported for participants participating in this study will be graded using the National Cancer Institute's (NCI) Common Terminology Criteria for Adverse Events (CTCAE), version 4.03. All AEs will be coded using the using MedDRA, version 20.0.

TEAE summary tables in both Part A and Part B will exclude sickle cell disease (SCD) related events defined as preferred terms of: combined acute chest syndrome and pneumonia, sickle cell anemia with crisis, osteonecrosis, and priapism. Additional select TEAE tables (Part B only) will summarize SCD related events which only include the preferred terms of acute chest syndrome and pneumonia (combined), sickle cell anemia with crisis, osteonecrosis, and priapism.

An overall summary will be presented which includes the number of TEAEs and the number and percentage of participants who experienced at least one TEAE. This summary will also include TEAEs Grade 3 or greater, TEAEs possibly/probably related to study drug, TEAEs leading to study drug reduction, TEAs leading to discontinuation of study drug, serious adverse events (SAEs), and deaths.

Additional summaries of TEAEs will be provided showing the number and percentage of participants who experienced at least one TEAE. These summaries will be presented by system organ class (SOC), preferred term (PT) and maximum severity. If a participant reports the same PT multiple times within the same SOC, that PT will only be counted once within that SOC for

that participant. As with the PT, if a participant reports multiple conditions within the same SOC, that SOC will only be counted once for that participant. In the summary, SOC will be listed in ascending alphabetical order; PTs will be listed in order of descending frequency for all participants within each SOC.

The occurrence of TEAEs possibly/probably related to GBT440 will be tabulated by SOC, PT and maximum severity. Serious adverse events will be presented by system organ class (SOC), preferred term (PT) and maximum severity.

Adverse events recorded in the eCRF which began prior to first dose of study drug will not be included in the summary tables.

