#### **5.2.2. Missing Start and Stop Dates for Adverse Events**

For missing start day only: day will be imputed as the first day of the month (i.e., 1) with the following exception: If the partial date falls in the same month and year as the treatment start date then the adverse event start date will be imputed as the treatment start date.

For missing stop day only: day only will be imputed as the last day of the month (i.e., 28, 29, 30, or 31).

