Adverse events recorded in the electronic case report form (eCRF) which began prior to first dose of study drug will not be included in the summary tables.

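### Part D (and Parts A/B) date an adverse event with no start day to the day before dosing, which removes it from the TEAE tables that are Part D's primary endpoint

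*SAP*

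**What the plan says.** The three SAPs handle the same situation, an adverse event with a missing start day in the month and year of first dose, in two ways.

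- **Part D SAP, 6.2.2:** "the adverse event start date will be imputed as the day prior to the treatment start date".
- **Parts A/B SAP, 6.2.3:** "then the adverse event start date will be imputed as the day prior to the treatment start date".
- **Part C SAP, 5.2.2:** "then the adverse event start date will be imputed as the treatment start date".

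The Part D definition of a TEAE (section 5) covers an event "that emerges on or after initiation of study drug (having been absent pre-treatment), or an AE that existed pre-treatment and worsened on treatment". Section 8.3.2 of the Part D SAP adds that events "which began prior to first dose of study drug will not be included in the summary tables". The Parts A/B SAP has the same exclusion in its own 8.3.2: "Adverse events recorded in the eCRF which began prior to first dose of study drug will not be included in the summary tables".

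Protocol 3.9.4.1 gives the Part D primary endpoint as "TEAEs and SAEs", and section 4.1 of the Part D SAP agrees. In Parts A and B, TEAEs are a safety endpoint, not the primary one.

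**The concern.** Imputation and exclusion are harmless apart but not together. The imputation places the event before first dose, and the exclusion then removes it. Neither step considers whether the investigator judged the event drug-related, whether it was serious, or whether a stop date shows it was still present after dosing.

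The exclusion in Part D refers to the summary tables in general, so SAE tables are exposed as well as TEAE tables. In the Part C SAP (7.3.2) the corresponding sentence is limited to TEAE tables.

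At stake is the primary safety result in the youngest children in the study, during the first weeks of exposure. The rule can remove a true on-treatment event but cannot add one. The same record would also be a TEAE in Part C and not in Part D, so rates from the two parts are not derived alike.

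**Working it through.** The plan states no figure on this point, so there is nothing to reproduce. The check applies the rules to example dates and then gives a scale.

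**1. The rules applied.** Take an event recorded with month March and no day. Study Day = event date − Day 1 date + 1 (Part D SAP, section 5).

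| First dose | Parts A/B and D: imputed date (formula result) | Counted? | Part C: imputed date (formula result) | Counted? |
|---|---|---|---|---|
| 1 March 2022 | 28 February (0) | No | 1 March (1) | Yes |
| 15 March 2022 | 14 March (0) | No | 15 March (1) | Yes |
| 31 March 2022 | 30 March (0) | No | 31 March (1) | Yes |

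The first row is wrong on its face. With dosing on 1 March, every possible March onset is on or after the dosing date, yet the assigned date lies in February and contradicts the month that was recorded.

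**2. Exceptions that might rescue the event.** The worsening clause in the TEAE definition covers events that existed before treatment and worsened; it does not cover a new event. The Parts A/B definition (section 4) treats Day 1 events as treatment-emergent, but the imputed date falls before Day 1, so that sentence never applies. The Part D definition has no such sentence.

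**3. Consistency within Part D.** The medication rule in 6.2.1 of the Part D SAP imputes the treatment start date in the same situation. If both start days are unknown, a medicine given for the event is dated Day 1 and the event itself the day before.

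**4. Share of the month at risk.** For first dose on day d of a 30-day month, the share of days on or after dosing is (31 − d)/30. If every d is equally likely, the mean is 15.5/30 = 51.7%, with a range from 1/30 = 3.3% to 30/30 = 100%. If event reporting began only 14 or 7 days before dosing, the mean share rises to 55% or 65%. The rule assigns 0% in every case.

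**5. Weight of one participant.**

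- Part D, about 30 participants: 1/30 = 3.3 points. For example, 2/30 (6.7%) is reported as 1/30 (3.3%).
- Part D, age group of 10 (the minimum for 6 months to under 2 years, protocol 3.1.4): 1/10 = 10 points.
- Part A, about 6 per cohort: 1/6 = 16.7 points.

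**6. Reach in Part A.** Follow-up runs from Day 1 to Day 15. The days falling in the dosing month are min(15, 31 − d). Averaged over d = 1 to 30 this is (16 × 15 + 105)/30 = 11.5 days, or 77% of the 15, so the rule covers most of the observation period.

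**The case against.** The strongest reply is that the rule will rarely operate. It needs a missing day, a known month and year, and a match with the first-dose month; a missing day in a later month goes to the 1st of that month and still counts. Part D reviews adverse events at Screening, Day 1, Week 2 and Week 4. Data are generally entered within five business days and checked against source, and SAEs are reported within 24 hours of site knowledge. Partial dates, especially for SAEs, may be few. This stands as a limit on size.

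Second, events are collected from consent and screening can last 35 days, so some undated events are truly pre-dose and are rightly excluded. That also stands. It argues for using the stop date where there is one, not for calling every such event pre-treatment.

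Third, the percentages above are arithmetic, not bias estimates. A participant with another event in the same row is still counted there, because each preferred term and organ class counts once per person. This is correct.

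Fourth, Part D is descriptive, with no test or threshold, no comparison of Parts C and D is planned, and the Parts A/B SAP lists adverse events in full for the Safety population. But a descriptive primary endpoint consists of its counts, and a listing does not correct a table. The Part D SAP text names no adverse event listing.

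None of these points cancels the mechanism, and no other text in the documents does.

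**Conclusion.** The concern holds. As written, the Part D and Parts A/B SAPs classify every new adverse event with a missing start day in the first-dose month as pre-treatment and drop it from the summary tables. In Part D those tables report the primary endpoint. The direction is fixed: towards under-counting. The size cannot be stated, because the number of such records is not given; it is zero if there are none, and up to 3.3 points per affected participant in Part D overall. The 52% share rests on assumed uniform onset and uniform dosing day. The conclusion about direction does not depend on either assumption. The rule should be changed because it acts on a primary safety endpoint, gives an impossible date when dosing falls on the 1st, and conflicts with the sponsor's own Part C rule.

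**What to change.** In Part D SAP 6.2.2 and Parts A/B SAP 6.2.3, replace the exception with the Part C rule: if the partial date falls in the month and year of first dose, impute the treatment start date. Add one guard, which the Part C SAP does not have: if a complete stop date precedes first dose, the event stays pre-treatment. For consistency, add the same guard to Part C 5.2.2.

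Add to the Part D TEAE definition the sentence found in the other two SAPs that events occurring on Day 1 are assumed treatment-emergent. This is a clarification; the imputation rule is the substantive change.

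The cost is a sentence or two in each SAP and a small change to the date derivation. The Parts A/B SAP serves an interim report from a database snapshot, so any tables already produced would need a re-run, or at least a count of the records affected. A few truly pre-dose events may be counted as TEAEs, which is the conservative direction for safety.

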## 7. ANALYSIS POPULATIONS

### 7.1. Efficacy Evaluable Population

All subjects who receive at least one dose of study drug will be included in the Efficacy Evaluable population (EE). All efficacy analyses will be based on the EE population.

In this study (GBT440-007 Part D), the EE population is the same as the Safety Population (see Section 7.2).

### 7.2. Safety Population

The Safety Population is defined as all subjects who receive at least one dose of study drug. This population will be used in the assessment and reporting of safety data.

### 7.3. PK Population

For the Population PK analysis, an individual will be defined as evaluable if both of the following criteria are satisfied:

1. Received at least 1 dose of voxelotol with associated dosing date and time

2. Has at least 1 measurable voxelotor concentration observation in plasma or whole blood with associated sampling time and dosing information

Details on PK analyses, as well as Hb occupancy, are provided in a separate analysis plan.

## **8. STATISTICAL METHODS**

Statistical analyses will be performed using SAS® Version 9.4 or higher.

Continuous variables will be descriptively summarized using number of subjects (n), mean, standard deviation (SD), median, minimum, maximum, and, as appropriate, 95% confidence intervals (CIs). Categorical variables will be descriptively summarized by presenting the number (frequency) and percentage in each category.

In general, results for Part D will be presented by age group (6 months to < 2 years and 2 years to < 4 years) and overall, as appropriate.

### **8.1. Subject Disposition, Demographic and Baseline Characteristics**

#### **8.1.1. Subject Disposition**

Subject disposition will be presented in terms of the numbers and percentages of subjects who completed the treatment and discontinued from treatment. The reasons for early treatment discontinuation will be presented. Similar summaries will be presented for subjects who discontinue study.

#### **8.1.2. Demographic and Baseline Characteristics**

The demographic variables collected in this study include age (months or years) at Screening, sex, race, and ethnicity and will be summarized descriptively. Height (cm), weight (kg), and BMI ( $\text{kg}/\text{m}^2$ ) at Day 1 will be presented using descriptive statistics. Subjects who record more than one race will be grouped into a single category denoted as multi-racial.

#### **8.1.3. Baseline Sickle Cell Disease Characteristics**

Number of VOCs including the number of VOCs requiring hospitalization and the number of blood transfusions during the previous 12 months will be summarized categorically.

Additional summaries including the number and percentage of subjects who currently use HU, who have each genotype (homozygous hemoglobin SS [HbSS] or hemoglobin S beta thalassemia [HbS β thal]), and who experienced a sickle cell complication prior to study enrollment will be presented. Baseline lab values including Hb, hemoglobin – fetal (HbF), and reticulocyte count will be summarized using descriptive statistics.

#### **8.1.4. Medical History Excluding Sickle Cell History**

Medical history excluding sickle cell history will be summarized by System Organ Class (SOC) and Preferred Term (PT) according to Medical Dictionary for Regulatory Activities (MedDRA), coding dictionary (current version).

## 8.2. Efficacy Analysis

All efficacy data will be summarized using the EE population.

Hematology and hemolysis parameters (hemoglobin, reticulocyte count, indirect bilirubin, and LDH) will be summarized at Week 24 and Week 48 in addition to each visit for observed values and changes (absolute and percent, as appropriate) from baseline using appropriate descriptive statistics. If indirect bilirubin is missing and direct and total bilirubin are collected, indirect can be calculated as:

$$\text{Indirect Bilirubin} = \text{Total Bilirubin} - \text{Direct Bilirubin}.$$

Hb response, defined as an increase in Hb  $> 1$  g/dL, will be summarized descriptively at Week 24 and Week 48 with 95% confidence intervals provided for the response rates. Subjects who drop-out early or do not have a Week 24 or Week 48 assessment, are not included in the analysis for Hb response. Additional response assessments at each visit will be summarized descriptively. No missing data imputation or adjustment for RBC transfusion will be performed for this endpoint.

Additionally, Hb response at Week 24 and Week 48 with 95% confidence intervals will be summarized using the treated population. All subjects treated will be included in the denominator for Hb response, and subjects without a Week 24 or Week 48 assessment will be counted as non-responders at each relevant timepoint.

For subjects who had a Hb response at least 1 visit, the time to the first response will be summarized descriptively (ie, median, first quartile, third quartile, and range).

The annualized incidence rates for VOC and stroke and the associated 95% CIs will be presented. Annualized rate is defined as the total number of events divided by total person years. Total person-years is defined as the sum of subject treatment period in years which covers the time from first dose to last dose. VOC is defined based on clinical review of adverse event MedDRA preferred terms (eg, sickle cell anemia with crisis, acute chest syndrome, and pneumonia).

Exploratory analysis for change from baseline to Weeks 24 and 48 in height, weight, and head circumference, will be summarized using continuous descriptive statistics at each visit.

## 8.3. Safety

All safety analyses will be conducted using the Safety Population.

### 8.3.1. Summary of Exposure

The duration of study drug exposure and actual study drug exposure will be summarized with descriptive statistics.

The number and percentage of subjects who permanently discontinued study drug, and the reason for discontinuation (AE or other) will be summarized. The number and percentage of subjects who missed at least 1 dose of study drug or had at least 1 dose reduction will be summarized. The summary will include the number and percentage of subjects who had a dose reduction or dose missed due to an adverse event or other reason. Additionally, the number and percentage of subjects will be summarized in categories of number of missed doses and number of dose reductions.

